
 Inadequate organ function demonstrated by any of the following, unless approved by the medical monitor: 
 Part 1 and Part 3: 
 Total bilirubin > upper limit of normal (ULN; except total bilirubin > ULN is acceptable if direct bilirubin is $\leq 1.2 \times$ ULN. Subjects with Gilbert's syndrome who have total bilirubin $\leq 2 \times$ ULN may be enrolled with medical monitor approval). Aspartate aminotransferase (AST) or alanine aminotransferase (ALT) > $1.5 \times$ ULN. Creatinine clearance < 50 mL/min (< 30 mL/min for MM) based on Cockcroft-Gault formula or 24-hour urine analysis. Part 2 and Part 4: 
 Total bilirubin > ULN (except total bilirubin > ULN is acceptable if direct bilirubin is $\leq 1.2 \times$ ULN. Subjects with Gilbert's syndrome who have total bilirubin $\leq 2 \times$ ULN may be enrolled with medical monitor approval). AST or ALT > $1.5 \times$ ULN. Creatinine clearance < 40 mL/min (< 30 mL/min for MM) based on Cockcroft-Gault formula or 24-hour urine analysis. Receipt of anticancer medications or investigational drugs within the following interval before the first administration of study drug (note: subjects enrolling in C-TGC must continue to receive their ruxolitinib throughout the study): 
 < 5 half-lives or 14 days, whichever is longer, for any investigational agent. < 28 days for any antibodies or biological therapies. < 5 half-lives for all other nonbiologic anticancer medications, or sponsor approval. < 6 weeks for mitomycin-C or nitrosoureas. The following are allowed: hydroxyurea for controlling proliferative disease and low-dose corticosteroids (prednisone or equivalent ≤ 10 mg per day). Hydroxyurea should not be used within 48 hours before and on the day of PD sample collection or during or 72 hours before or after azacitidine administration. Note: Concomitant hydroxyurea is prohibited in subjects with MF within 8 weeks before enrolling (Day 1) into C-TGC. Unless approved by the medical monitor, may not have received an allogeneic hematopoietic stem cell transplant within 6 months before treatment, or have active graft-versus-host disease following allogeneic transplant, or have received immunosuppressive therapy (including, but not limited to, cyclosporine, tacrolimus, mycophenolate mofetil, or corticosteroids [> 10 mg/day prednisone equivalent]) following allogeneic transplant within 2 weeks of Cycle 1 Day 1. Unless approved by the medical monitor, may not have received autologous hematopoietic stem cell transplant within 3 months before treatment. 			

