3.3. Subject Exclusion Criteria

A subject who meets any of the following criteria will be excluded from the study:

1. Inadequate bone marrow function demonstrated by any of the following:

Laboratory Parameter	TGB (Part 1)	TGB (Part 2)	C-TGC (Parts 3 and 4)
Hemoglobin (g/dL)	< 8.0	< 8.0	Subjects unwilling to receive red blood cell transfusions to treat low hemoglobin levels are excluded.
Platelets ($\times 10^9/L$)	< 75	< 50	< 50 in 2 weeks before screening or platelet transfusions within 4 weeks of screening.
Absolute neutrophils ($\times 10^9/L$)	< 1.0	< 1.0	< 0.5 in the 2 weeks before screening.

Note: No specific hematologic exclusion criteria apply for TGA (Parts 1 and 2), Part 3 C-TGA and C-TGB, and Part 4 C-TGA E1 and C-TGB E1 cohorts.

CONFIDENTIAL

CONFIDENTIAL

2. Inadequate organ function demonstrated by any of the following, unless approved by the medical monitor:
 - Part 1 and Part 3
 - a. Total bilirubin > upper limit of normal (ULN; except total bilirubin > ULN is acceptable if direct bilirubin is $\leq 1.2 \times$ ULN. Subjects with Gilbert's syndrome who have total bilirubin $\leq 2 \times$ ULN may be enrolled with medical monitor approval).
 - b. AST or ALT > $1.5 \times$ ULN.
 - c. Creatinine clearance < 50 mL/min (< 30 mL/min for MM) based on Cockcroft-Gault formula or 24-hour urine analysis.
 - Part 2 and Part 4
 - d. Total bilirubin > ULN (except total bilirubin > ULN is acceptable if direct bilirubin is $\leq 1.2 \times$ ULN. Subjects with Gilbert's syndrome who have total bilirubin $\leq 2 \times$ ULN may be enrolled with medical monitor approval).
 - e. AST or ALT > $1.5 \times$ ULN.
 - f. Creatinine clearance < 40 mL/min (< 30 mL/min for MM) based on Cockcroft-Gault formula or 24-hour urine analysis.
3. Receipt of anticancer medications or investigational drugs within the following interval before the first administration of study drug (note: subjects enrolling in C-TGC must continue to receive their ruxolitinib throughout the study):
 - a. < 5 half-lives or 14 days, whichever is longer, for any investigational agent.
 - b. < 28 days for any antibodies or biological therapies.
 - c. < 5 half-lives for all other nonbiologic anticancer medications, or sponsor approval.
 - d. < 6 weeks for mitomycin-C or nitrosoureas.

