5.2.4. Criteria and Procedures for Dose Interruptions and Adjustments of Study Drug

Treatment with INCB053914, L-DAC, azacitidine, or ruxolitinib may be delayed up to 2 weeks (≤ 14 days) to allow for resolution of toxicity. The second induction or consolidation cycles of I-DAC may be delayed until subject has recovered from I-DAC-related toxicities. Subjects may resume treatment if no medical condition or other circumstance exists that, in the opinion of the investigator, would make the subject unsuitable for further participation in the study. The treating investigator should contact the sponsor to discuss the case of any subject whose treatment has been delayed for more than 14 days before restarting treatment with INCB053914, L-DAC, azacitidine, or ruxolitinib.

Because subjects may enter the study with extensive pretreatment and/or severe bone marrow infiltration by the primary disease, these dose reduction rules are provided as guidelines (see [Table 5](#)). Individual decisions regarding dose reduction should be made using clinical judgment and in consultation with the sponsor's medical monitor, taking into account relatedness of the AE to the study drug or SOC agents, and the subject's underlying condition. Adverse events that have a clear alternative explanation or transient (≤ 72 hours) abnormal laboratory values without associated clinically significant signs or symptoms may be exempt from dose-reduction rules. Hematologic events (eg, thrombocytopenia, anemia, neutropenia) occurring in Part 1 TGB precipitating dose interruptions during Cycle 1 of treatment will be evaluated as potential DLTs ([Table 4](#)) and managed as per the guidelines in Section 5.2.3. Hematologic AEs that precipitate dose interruptions should be monitored for recovery at least every 3 days, if feasible.

CONFIDENTIAL

CONFIDENTIAL

Table 5: Guidelines for Interruption and Restarting of Study Drug

CHEMISTRY		
Adverse Event	Trigger	Action Taken
ALT and/or AST elevation	Grade 1	
 Continue study drug: 
 –Monitor LFTs at least weekly until < Grade 1 or baseline. –Carefully examine subject's concomitant medications for any that may contribute to LFT elevations. Hold these concomitant medications or switch to an alternative; consult medical monitor if needed. –Subjects with persistent but stable low-grade elevations (eg, < 1.5 × ULN) may revert to the routine LFT evaluation schedule as noted in Section 6.

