	Grade 2	
 Continue study drug: 
 –Take actions as noted for Grade 1 elevations until LFTs have resolved to ≤ Grade 1 or baseline. –Refer to Appendix S for PHL case evaluation. –If Grade 2 elevation lasts ≤ 14 days, no action required. –If Grade 2 elevation lasts > 14 days, interrupt drug, monitor LFTs at least weekly, AND: 
 ▪ If resolved within 14 days after interruption, resume study drug at the same dose, monitor LFTs at least weekly during the next month and according to Protocol schedule thereafter. ▪ If LFTs do not resolve to ≤ Grade 1 or baseline within 14 days after interruption lasts, discuss with medical monitor.
	Grade 3 or 4	
 Refer to Appendix S for PHL case evaluation Complete a coagulation panel on the subject. Interrupt study drug and monitor LFTs at least weekly until ≤ Grade 1 or baseline: 
 –If resolved within 14 days after interruption subject may resume study drug at next lower dose (or at 25% reduction [Part 2 or Part 4], rounded down to the nearest strength). –If LFTs do not resolve to ≤ Grade 1 or baseline within 14 days after interruption, discuss with medical monitor. Carefully examine subject's concomitant medications for any that may contribute to LFT elevations. Hold these concomitant medications or switch to an alternative; consult medical monitor if needed.
Total bilirubin elevation	> 2 × ULN	
 Refer to Appendix S for PHL case evaluation If > 3 × ULN, interrupt treatment.
ALT and/or AST > 3.0 × ULN AND total bilirubin > 2.0 × ULN (Hy's law)		
 Interrupt treatment Refer to Appendix S for PHL case evaluation

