		Female subjects of childbearing potential require a serum test at screening. Pregnancy tests (serum or urine) should be repeated during the study as required by local regulations.
		Coagulation Panel
		PT aPTT INR
LFT Panel	Lipids	Urinalysis With Microscopic Examination
Alkaline phosphatase ALT AST Total bilirubin Direct bilirubin ^e	Total cholesterol Triglycerides LDL HDL	Color and appearance pH and specific gravity Bilirubin Glucose Ketones Leukocytes Nitrite Occult blood Protein Urobilinogen

aPTT = activated partial thromboplastin time; HDL = high-density lipoprotein; INR = international normalized ratio; LDL = low-density lipoprotein; PT = prothrombin time.

[figure not shown]
^a HbA1c to be performed on all Part 1 and Part 3 subjects at screening only.

^b Absolute values must be provided for lymphocytes and neutrophils.

^c Required at intervals specified in [Table 6](#), [Table 9](#), [Table 12](#), [Table 15](#), and [Table 18](#) for diseases where peripheral blast count is part of disease assessments such as AML, MDS, MDS/MPN, and MF.

^d Screening hepatitis B and C viral loads by PCR assay are required for all ruxolitinib combination subjects (C-TGC). For all other subjects, hepatitis B and C viral loads by PCR assay only need to be assessed when respective serology results are positive. Hepatitis B virus DNA does not need to be performed if the HBV surface antibody is the only positive result (indicating immunity due to vaccination).

^e Direct bilirubin should only be performed when total bilirubin is > ULN and subject does not have Gilbert's syndrome.

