8. SAFETY MONITORING AND REPORTING

8.1. Adverse Events

8.1.1. Definitions

For the purposes of this Protocol, an adverse event (AE) is defined as the appearance of or worsening of any pre-existing undesirable sign, symptom, or medical condition that occurs after a subject provides informed consent. Abnormal laboratory values or test results occurring after informed consent constitute AEs only if they induce clinical signs or symptoms, are considered clinically meaningful, require therapy (eg, hematologic abnormality that requires transfusion), or require changes in the study drug(s).

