APPENDIX S. MANAGING POTENTIAL HY'S LAW CASES

INTRODUCTION

During the course of the study the investigator will remain vigilant for increases in liver biochemistry. The investigator is responsible for determining whether a subject meets potential Hy's law (PHL) criteria at any point during the study.

The investigator participates, in conjunction with Incyte clinical project and pharmacovigilance representatives, in the review and assessment of cases fulfilling PHL criteria to ascertain whether there is an alternative explanation for the elevations in liver biochemistry other than drug-induced liver injury caused by the study drug.

The investigator fulfils requirements for the recording of data pertaining to PHL or Hy's law cases and AE/SAE reporting according to the outcome of the review and assessment in line with standard safety reporting processes.

DEFINITIONS

For the purpose of this process definitions are as follows

Potential Hy's Law (PHL)

An increase in AST or ALT $> 3 \times$ ULN and total bilirubin $> 2 \times$ ULN at any point during the study. The elevations do not have to be at the same time or within a specified time frame.

Hy's Law

An increase in AST or ALT $> 3 \times$ ULN and total bilirubin $> 2 \times$ ULN, where no other reason can be found to explain the combination of increases, eg, elevated serum ALP indicating cholestasis, viral hepatitis, another drug.

ACTIONS REQUIRED IN CASES OF AST OR ALT $> 3 \times$ ULN OR TOTAL BILIRUBIN $\geq 2 \times$ ULN

Identification and Determination of Potential Hy's Law

To identify cases of AST or ALT $> 3 \times$ ULN or total bilirubin $> 2 \times$ ULN and consequently determine whether the subject meets PHL criteria, please follow the instructions below:

- Review the laboratory report and if a subject has AST or ALT $> 3 \times$ ULN OR total bilirubin $> 2 \times$ ULN at any visit:
 - Determine without delay whether the subject meets PHL criteria by reviewing laboratory reports from all previous visits.
 - Enter the laboratory data into the laboratory CRF as soon as possible.

CONFIDENTIAL

CONFIDENTIAL

Potential Hy's Law Criteria Not Met

If the subject has NOT had AST or ALT $> 3 \times$ ULN AND total bilirubin $> 2 \times$ ULN at any point in the study (the elevations do not have to be at the same time or within a specified time frame), irrespective of ALP, please follow the instruction below:

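### Bilirubin entry rule has no ceiling for subjects without Gilbert's syndrome, so some can enrol above the protocol's own liver action levels without medical monitor approval

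*Protocol*

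**What the plan says.** The stem of exclusion criterion 2 (Protocol Section 3.3) reads: "Inadequate organ function demonstrated by any of the following, unless approved by the medical monitor". Under it, criteria 2a (Parts 1 and 3) and 2d (Parts 2 and 4) exclude total bilirubin above ULN, "except total bilirubin > ULN is acceptable if direct bilirubin is" ≤ 1.2 × ULN. The next sentence deals with Gilbert's syndrome: total bilirubin up to 2 × ULN may be enrolled with medical monitor approval. The synopsis has the same text.

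Table 21, footnote e, settles who uses which route: "Direct bilirubin should only be performed when total bilirubin is > ULN and subject does not have Gilbert's syndrome". The direct-bilirubin exception is thus the route for subjects without Gilbert's.

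On study, the total bilirubin row of Table 5 (Section 5.2.4) sends values above 2 × ULN to Appendix S for PHL evaluation, and adds: "If > 3 × ULN, interrupt treatment". Appendix S defines PHL as ALT or AST above 3 × ULN and total bilirubin above 2 × ULN at any point in the study: "The elevations do not have to be at the same time or within a specified time frame".

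**The concern.** The exception names no maximum total bilirubin. Because a subject covered by it is not excluded, the stem's approval clause does not apply. The result is lopsided. A Gilbert's subject at 1.5 × ULN, whose elevation already has a diagnosis, needs approval. A subject without Gilbert's at 2.5 or 3.5 × ULN, possibly with no diagnosis, does not.

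This matters because the liver is the organ the protocol watches most closely. Section 1.4.1 gives hepatotoxicity as the main animal toxicity, Section 1.4.2.1 reports ALT/AST elevations of Grade 3 or higher in three subjects, and Section 1.4.4 names ALT/AST elevation as the expected adverse event. At stake is the reading of a later transaminase rise. Once PHL criteria are met, drug is interrupted and the medical monitor is contacted. If no alternative explanation is agreed, drug is stopped permanently and an SAE assessed as related is reported.

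**Working it through.** No sample size or error rate is involved. The check reads the entry rule as a logical condition and compares it with the on-study levels.

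**1. Does the direct-bilirubin limit imply a limit on the total?** Total = direct + indirect, and the rule does not restrict the indirect part. The documents give no ratio between the two ULNs. Assume the direct ULN is 0.15 to 0.40 of the total ULN. Direct bilirubin at its limit is then 1.2 × 0.15 = 0.18 to 1.2 × 0.40 = 0.48 of the total ULN, and the remainder is open-ended. Reading 1.2 × ULN against the total ULN leaves the indirect part just as open.

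**2. Is there a cap elsewhere?**
- Criterion 23 excludes subjects at significant risk, in the investigator's judgment.
- Criterion 6 concerns unresolved toxicity from earlier anticancer therapy.
- Section 1.4.3.2 says that subjects with significant baseline hepatic impairment are excluded.
- Sections 6.1 and 6.2.1 have screening results reviewed before enrolment and again on Day 1.

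None of these sets a bilirubin value or a medical monitor step.

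**3. Worked cases**, for a subject without Gilbert's and with direct bilirubin ≤ 1.2 × ULN. The entry values are illustrations.

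| Total bilirubin at entry (× ULN) | Approval needed now | Change needed to exceed 2 × ULN | Above 3 × ULN at entry | Approval needed under the fix |
|---|---|---|---|---|
| 1.0 | No | 2.0/1.0: more than a 2-fold rise | No | No |
| 1.9 | No | 2.0/1.9 = 1.053: a rise of just over 5% | No | No |
| 2.5 | No | None; 2.0/2.5 = 0.80, so a 20% fall to return to 2 × ULN | No | Yes |
| 3.2 | No | None | Yes; 3.0/3.2 = 0.94, so about a 6% fall to return to 3 × ULN | Yes |

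**4. What PHL then requires.** The ALT/AST entry limit is 1.5 × ULN and the PHL level is above 3 × ULN, so 3.0/1.5 = 2: a subject at or below the limit must more than double. A subject entering at 1.0 × ULN bilirubin needs that rise and also more than a doubling of bilirubin. A subject entering at 2.5 × ULN needs only the ALT/AST rise. A later fall in bilirubin does not undo this, because the two elevations need not coincide and Appendix S has sites review reports from all previous visits.

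**5. DLT evaluability (Parts 1 and 3).** Sections 4.3.2 and 5.2.3 require 80% of first-cycle doses.
- 21-day cycle, twice daily: 42 doses; 0.80 × 42 = 33.6, so at least 34 taken and at most 8 missed, or 4 days.
- 28-day cycle: 56 doses; 0.80 × 56 = 44.8, so at least 45 taken and at most 11 missed, or 5.5 days.

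A longer hold in Cycle 1 would make a subject without a DLT non-evaluable. This matters only if a site holds drug for a bilirubin value it already knew at enrolment.

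**The case against.** The strongest defence is that the rule is a sensible clinical choice. Section 1.4.1 places the animal liver effects mainly in the bile ducts. Limits of 1.2 × ULN on direct bilirubin and 1.5 × ULN on ALT/AST screen for that kind of injury, leaving open mainly isolated indirect elevation, which the documents do not show to raise drug risk. That stands as a reason for the exception, but it does not explain why only the Gilbert's route has a ceiling and an approval step.

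Several stronger readings are tempting, and the documents do not support them:

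- *Anyone entering above 3 × ULN must be interrupted at once.* Section 5.2.4 says "these dose reduction rules are provided as guidelines", to be applied with clinical judgment and in consultation with the medical monitor. The Table 5 rows concern adverse events, defined in Section 8.1.1 as "the appearance of or worsening of any pre-existing undesirable sign, symptom, or medical condition that occurs after a subject provides informed consent". A stable value from before consent arguably falls outside that definition. "Adverse events that have a clear alternative explanation" may also be exempt.
- *The baseline bilirubin goes unexamined until ALT or AST rises.* Appendix S already asks for a PHL check, without delay, at any visit with bilirubin above 2 × ULN. Only the joint review waits for the second half. The screening direct bilirubin is itself evidence for an alternative explanation, and Section 8.7 provides regular subject-by-subject calls.
- *Liver injury could be missed.* The effect runs the other way, towards earlier interruption and review.
- *DLT evaluability is threatened.* This would need a rare subject, an investigator who enrols despite criterion 23, and then a hold for the same known value.

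It is also fair to say that the fix removes no trigger for an approved subject and does nothing for one at 1.9 × ULN.

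**Conclusion.** The gap is real on the text: for a subject without Gilbert's syndrome whose direct bilirubin is ≤ 1.2 × ULN, no provision caps total bilirubin at entry or calls for medical monitor approval. It goes beyond preference because the rule admits subjects already above levels at which the same protocol calls for PHL evaluation or interruption.

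The consequence is small. It is a possible false-positive PHL case when a transaminase rise, which is expected with this drug, follows a bilirubin elevation that was present at entry. The documents do not say how many subjects would enter this way; the number is probably very small, and no rate is assumed here. No efficacy endpoint or Simon stopping rule is involved. The conclusion rests on reading the exception literally, which Section 3 supports by allowing no deviations from the eligibility criteria. This is a cheap improvement, not a necessary correction.

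**What to change.** In criteria 2a and 2d and the matching synopsis text, insert *and ≤ 2 × ULN* after > ULN inside the exception, so that it covers only total bilirubin above ULN and up to 2 × ULN with direct bilirubin ≤ 1.2 × ULN. The protocol already uses 2 × ULN as the Gilbert's cap and the PHL bilirubin threshold.

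Above 2 × ULN the existing stem still permits entry with medical monitor approval. The baseline cause, and how the Table 5 and PHL triggers will be handled, are then agreed before the first dose. Tables 4 and 5, Appendix S and the SAP stay as they are. No test is added and nobody is barred outright.

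The cost is an occasional extra approval request. The triggers still apply to approved subjects, entry just below 2 × ULN is unaffected, and the approval step for Gilbert's subjects between 1 and 2 × ULN stays as it is.

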CFR	Code of Federal Regulations
CLL	chronic lymphocytic leukemia
C _{max}	maximum observed plasma or serum concentration
CMML	chronic myelomonocytic leukemia
CNS	central nervous system
CR	complete response/remission
CRc	cytogenetic complete remission
CRi	complete remission with incomplete recovery
CRm	molecular complete remission
CT	computed tomography
CTCAE	Common Terminology Criteria for Adverse Events
C-TGA	Combination Treatment Group A
C-TGA E1	Combination Treatment Group A Expansion Cohort 1
C-TGA E2	Combination Treatment Group A Expansion Cohort 2
C-TGB	Combination Treatment Group B
C-TGB E1	Combination Treatment Group B Expansion Cohort 1
C-TGC	Combination Treatment Group C
C-TGC E1	Combination Treatment Group C Expansion Cohort 1
CYP	cytochrome P450
DLBCL	diffuse large B-cell lymphoma
DLT	dose-limiting toxicity

CONFIDENTIAL

CONFIDENTIAL

Term	Explanation
EBMT	European Group for Blood and Marrow Transplant
EDC	electronic data capture
EOT	end of treatment
ECG	electrocardiogram
ECOG	Eastern Cooperative Oncology Group
eCRF	electronic case report form
[REDACTED]	[REDACTED]
[REDACTED]	[REDACTED]
FDA	Food and Drug Administration
FDG	fluorodeoxyglucose
FDG-PET	positron emission tomography using [¹⁸ F] fluorodeoxyglucose
FISH	fluorescence in situ hybridization
FLC	free light chain
GCP	Good Clinical Practice
GLP	Good Laboratory Practices
GOLD	Global Initiative for Chronic Obstructive Lung Disease
HbA1c	hemoglobin A1c
HBV	hepatitis B virus
HBV-DNA	hepatitis B virus deoxyribonucleic acid
HCV	hepatitis C virus
HCV-RNA	hepatitis C virus ribonucleic acid
HDL	high-density lipoprotein
HED	human equivalent dose
Hgb	hemoglobin
HIPAA	Health Insurance Portability and Accountability Act of 1996
HIV	human immunodeficiency virus
IB	Investigator's Brochure
IC ₅₀	half maximal inhibitory concentration
ICF	informed consent form
ICH	International Conference on Harmonisation
I-DAC	intermediate-dose cytarabine
IEC	independent ethics committee
IgM	immunoglobulin M
IL	interleukin
IN	Investigator Notification
INR	international normalized ratio

CONFIDENTIAL

CONFIDENTIAL

Term	Explanation
IRB	institutional review board
IMWG	International Myeloma Working Group
IWCLL	International Workshop on Chronic Lymphocytic Leukemia
IWG	International Working Group
IV	intravenously
L-DAC	low-dose cytarabine
LDi	longest diameter
LFT	liver function test
LDL	low-density lipoprotein
MDS	myelodysplastic syndrome
MDS/MPN-U	myelodysplastic/myeloproliferative neoplasms unclassifiable
MedDRA	Medical Dictionary for Regulatory Activities
MF	myelofibrosis
MM	multiple myeloma
MPN	myeloproliferative neoplasms
MRI	magnetic resonance imaging
MTD	maximum tolerated dose
ORR	objective remission rate
PAD	pharmacologically active dose
PASK	PAS kinase
pBAD	phosphorylated Bcl-2-associated death promoter protein
PD	pharmacodynamics
PET	positron emission tomography
PET-MF	post-essential thrombocythemia myelofibrosis
PHL	potential Hy's law
P-gp	P-glycoprotein 1
PIM	proviral integration site of Moloney murine leukemia virus
PK	pharmacokinetics
PMF	primary myelofibrosis
PPD	primary progressive disease
PPV-MF	post-polycythemia vera myelofibrosis
PR	partial remission
PRBC	packed red blood cells

CONFIDENTIAL

CONFIDENTIAL

Term	Explanation
PT	prothrombin time
QTcF	QT interval corrected using the Fridericia formula
QD	once daily
RARS-T	refractory anemia with ring sideroblasts and thrombocytosis
RBC	red blood cell
RD	resistant disease
RP2D	recommended Phase 2 dose
SAE	serious adverse event
SC	subcutaneously
SD	stable disease
SDi	smallest diameter
SOC	standard-of-care
SUSAR	suspected unexpected serious adverse reaction
TGA	Treatment Group A
TGA E1	Treatment Group A Expansion Cohort 1
TGA E2	Treatment Group A Expansion Cohort 2
TGA E3	Treatment Group A Expansion Cohort 3
TGB	Treatment Group B
TGB E1	Treatment Group B Expansion Cohort 1
TGB E2	Treatment Group B Expansion Cohort 2
TGC	Treatment Group C
T _{max}	time to maximum plasma concentration
ULN	upper limit of normal
UPM	unit probability mass
V _{dss}	volume of distribution at steady state
WBC	white blood cell

CONFIDENTIAL

CONFIDENTIAL

